**C.4.6 Response Inhibition Task for fMRI:** An event-related Go/NoGo task [1] is used for fMRI of response inhibition. In each run, the subjects look at a total of 224 visual stimuli that are sequentially presented in random order. Each stimulus is displayed for 500 ms, and any two neighbor stimuli are separated by a blank screen lasting 1900, 2100, or 2300 ms (uttered randomly). Each visual stimulus consists of lines enclosed within two boxes that are presented simultaneously side by side. The subjects are instructed to look at both boxes and to discriminate the direction of the lines. The subjects are instructed to press a button using their right index finger only when they see that both boxes show diagonal lines in the same direction in both boxes (Go trials). The subjects are instructed not to press any button when they see that both boxes show horizontal lines (easy-NoGo trials), or when they see that one box contains diagonal lines that are in the opposite direction of the diagonal lines in the other box (hard-NoGo trials). For Go trials, a correct response is defined as a key-press completed within 600 ms. For NoGo trials, an incorrect response is defined as a key-press completed within 600 ms. There are 168 Go trials (75%), 28 easy-NoGo trials (12.5%), and 28 Hard-NoGo trials (12.5%) in each fMRI run (10 min 40 s per run). For detailed descriptor, please see reference [1].

**C.4.7 Pre- and Post-treatment Behavioral Performance:** Because fMRI sessions in this project are conducted only during pretreatment baseline, this project will also acquire out-of-scanner pre-treatment and post-treatment (week 12) behavioral data for the cognitive tasks. Pre-treatment performance will be considered as a possible confounding factor and will be controlled as a covariate in the statistical analysis (Section C.4.20). Post-treatment behavioral performance is a treatment outcome and will be included in the treatment prediction analysis (C.4.20). In addition, [name], who is an expert in the behavioral science of drug addiction, will be a Consultant on this project to advise on the behavioral data implementation and analysis.

**C.4.8 MRI Scanning Site and Devices:** MRI sessions are conducted at the Magnetic Resonance Imaging Center of the UTHSC-H, using a research-dedicated Philips Intera 3.0 T MRI scanner with an 8-channel receive head coil (Philips Medical Systems, Best, Netherlands).

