**C.4.20 Statistical analysis:**

**Specific Aim 1:** To conduct an snOCM study of working memory to determine the baseline effective connectivity between OLPFC and striatum in treatment-seeking COs compared to non-drug using controls.

Initial analyses will evaluate group differences on demographic and baseline variables, will use contingency tables with chi-square testing, ANOVA's, and examination of correlations between baseline variables and snOCM results. The Friston et al. [189] network discovery technique, BMS, and BFLI (C.4.19.3) will be used to select the optimal model based on the exceedance probability of the OCM (or family of OCMs) in which OLPFC causally affects ventral striatum vs. exceedance probability of the OCM (or a family of OCMs) in which the ventral striatum causally affects the OLPFC. The parameter estimates for the endogenous OLPFC-striatal connectivity will be compared between groups using BMA and also compared using analysis of covariance.

**Specific Aim 2:** To determine whether the pretreatment gating effect by dorsal striatum on IFC-PPC effective connectivity (reflecting low OA) predicts treatment response to OA pharmacotherapy in COs.

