Urn randomization [153], a form of stratified randomization, will help ensure comparability of treatment groups on baseline severity and duration of cocaine abuse. Pretreatment task behavioral performance or demographic variables on which group differences are detected, and which are correlated with outcomes, meet the definition of confounders [192, 193]. In such cases, analyses will evaluate the robustness of findings after statistically controlling for the confounder. If conclusions remain unchanged after covarying for the confounder, the more parsimonious model will be reported along with a statement indicating its robustness to covariation for potential confounding. If inclusion of the covariate alters the conclusions of the analysis, both models will be reported. Treatment success is a function of two elements: (a) retention and (b) demonstrating cocaine-free status using the SRPHK1 criteria (see section C.3.4). The Treatment Effectiveness Score (TES) provides a metric for this composite outcome [194]. TES is the sum of all cocaine-negative tests (according to SRPHK1 rules). Higher TES indicates that participants both continue to participate in the study and are negative for cocaine. For each group, BMA (section C.4.19.4) is conducted across all OCMs in the model space. Group difference in the gating effect by the dorsal striatum is assessed using Bayesian confidence probability [195]. In addition, BMA is conducted across all OCMs in the model space for each subject in the medication group and in the placebo group. Evaluation of differential treatment response, measured by the TES, as a function of the averaged (across the OCM model space) gating effect, will use Poisson regression. Violations of assumptions of dispersion will result in the use of more appropriate approaches such as zero-inflated Poisson, negative binomial, or zero-inflated negative binomial models. Regression of treatment, averaged gating, and their interaction will permit evaluation of differential treatment response as function of gating. The critical element in doing so is the evaluation of the interaction term. Given that the current study is powered to detect group differences, it is likely underpowered to detect an interaction. Brookes, et al. [196] demonstrate that for studies with 80% power to detect a between-groups effect, power to detect an interaction effect of the same magnitude as the main effect is approximately 29%. One solution is to adopt a Bayesian subgroup analysis approach [197-201]. This approach utilizes the posterior distribution of the interaction parameter to estimate the

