Urn randomization, a form of stratified randomization, will help ensure comparability of treatment groups on baseline severity and duration of cocaine abuse. Pretreatment task behavioral performance or demographic variables on which group differences are detected, and which are correlated with outcomes, meet the definition of confounders. In such cases, analyses will evaluate the robustness of findings after statistically controlling for the confounder. If conclusions remain unchanged after covarying for the confounder, the more parsimonious model will be reported along with a statement indicating its robustness to covariation for potential confounding. If inclusion of the covariate alters the conclusions of the analysis, both models will be reported. Treatment success is a function of two elements: (a) retention and (b) demonstrating cocaine-free status using the SRPHK1 criteria. The Treatment Effectiveness Score (TES) provides a metric for this composite outcome. TES is the sum of all cocaine-negative tests (according to SRPHK1 rules). Higher TES indicates that participants both continue to participate in the study and are negative for cocaine. For each group, BMA is conducted across all DCMs in the model space. Group difference in the gating effect by the dorsal striatum is assessed using Bayesian confidence probability. In addition, BMA is conducted across all DCMs in the model space for each subject in the medication group and in the placebo group. Evaluation of differential treatment response, measured by the TES, as a function of the averaged (across the DCM model space) gating effect, will use Poisson regression. Violations of assumptions of dispersion will result in the use of more appropriate approaches such as zero-inflated Poisson, negative binomial, or zero-inflated negative binomial models. Regression of treatment, averaged gating, and their interaction will permit evaluation of differential treatment response as function of gating. The critical element in doing so is the evaluation of the interaction term. Given that the current study is powered to detect group differences, it is likely underpowered to detect an interaction. Brookes, et al. demonstrate that for studies with 80% power to detect a between-groups effect, power to detect an interaction effect of the same magnitude as the main effect is approximately 29%. One solution is to adopt a Bayesian subgroup analysis approach. This approach utilizes the posterior distribution of the interaction parameter to estimate the probability that it exceeds some number (e.g., for Poisson regression a Risk Ratio of 1.0). Specification of vague neutral priors will reflect uncertainty regarding parameter values, utilizing prior distributions for the lower order effects that are neutral and diffuse with specification  $\sim N(0, 1 \times 10^{-6})$  on the log scale (i.e., centered at the null hypothesis with a 95% Credible Interval of  $\pm 1960$ ) for all coefficients, and  $\sim U(0, 100)$  for any required dispersion terms. Examination of the interaction of treatment and the subgroup index forms the crux of the evaluation of the subgroup effect. For evaluating the interaction representing the differential subgroup effect, analysis will be conducted in two ways: (a) utilizing diffuse, indifferent priors ( $\sim N(0, 1 \times 10^{-6})$ ) on the log scale for the interaction coefficients, and (b) using informative skeptical priors for the coefficients will evaluate sensitivity of statistical conclusions to specification of priors. Informative, skeptical priors will be derived via the method first proposed by Dixon and Simon. Evaluation of resulting posterior distributions will permit conclusions regarding the probability that subgroup/interaction effects of varying magnitudes obtain. Examples of this use of the posterior distribution may be found in Green et al. (2009). Bayesian modeling will use SAS v9.2 (Proc Genmod and Proc Monte-Carlo Markov chain [MCMC]), and in WinBugs 1.4.3 (<http://www.mrc-bsu.cam.ac.uk/bugs>). Convergence of Bayesian analyses on the posterior distributions via MCMC will be assessed via graphical (Trace Plot, Autocorrelation Plot) and quantitative (Geweke Diagnostics, Gelman-Rubin Diagnostics, and Heidelberger-Welsh Diagnostics) evidence. Evaluation of posterior distributions will permit statements regarding the probability that effects of varying magnitudes exist, given the data.

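### Protocol C.4.7 promises pre-treatment task performance as a covariate for the week-12 performance outcome, but C.4.20 and the SAP admit it only on a detected group difference

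*Protocol*

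**What the plan says.** Three places bear on this.

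- **Protocol C.4.7** states that "this project will also acquire out-of-scanner pre-treatment and post-treatment (week 12) behavioral data for the cognitive tasks". On the later score it says "Post-treatment behavioral performance is a treatment outcome and will be included in the treatment prediction analysis (C.4.20"). On the earlier one it says "Pre-treatment performance will be considered as a possible confounding factor and will be controlled as a covariate in the statistical analysis (Section C.4.20"). No condition is attached to that covariate.
- **Protocol C.4.20, Specific Aim 2**, sets a different rule. The variables treated as confounders are "Pretreatment task behavioral performance or demographic variables on which group differences are detected, and which are correlated with outcomes". When both conditions are met, the covariate serves as a robustness check: "If conclusions remain unchanged after covarying for the confounder, the more parsimonious model will be reported". Both models are reported only if the covariate alters the conclusions.
- **The SAP, Data analysis plan**, repeats the C.4.20 rule and does not carry over the C.4.7 sentence.

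The only outcome regression written out in C.4.20 and the SAP is for the TES, by Poisson regression or a count-model alternative: "Regression of treatment, averaged gating, and their interaction will permit evaluation of differential treatment response as function of gating". Of this analysis C.4.20 says "The critical element in doing so is the evaluation of the interaction term". Neither document writes out a model for week-12 task performance. C.4.20 also lists "examination of correlations between baseline variables and snOCM results" among the initial analyses, but no adjustment follows from what is found.

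**The concern.** An analyst working from the SAP would normally model week-12 performance without its own baseline, although C.4.7 says the baseline will be there. A test for a group difference is the wrong gatekeeper for two reasons.

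1. **Precision.** A baseline score removes outcome variance whether or not the arms differ on it. Randomisation makes a difference unlikely to be detected, so the covariate is usually left out and its variance stays in the error term.
2. **Confounding of gating.** Gating is measured, not randomised. C.4.19.1 itself links striatal dopamine function, and connectivity from left inferior frontal to left posterior parietal cortex, to working-memory capacity. If gating tracks baseline ability, and ability persists to week 12, gating will correlate with week-12 performance even when it carries no further information. That relation exists inside each arm, so comparing the arms on baseline performance cannot reveal it.

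The stated objective is to predict treatment response from baseline connectivity. Persistence of ability could be reported as prediction.

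**Working it through.** **Inputs.** From the protocol: 24 usable scans per group after 20% loss from 30 recruited (C.4.1), and two-tailed alpha 0.05 (C.4.21). Assumed, because the documents give no values: the pre/post performance correlation rho, the gating-baseline correlation r, and a normal outcome.

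**The plan's own figure.** C.4.21 states 86% power for a correlation of 0.60 with 24 subjects. The pilot used Spearman correlation, so power = Φ(atanh(0.60) × √(21/1.06) − 1.96) = Φ(0.693 × 4.451 − 1.96) = Φ(1.125) = 87.0%. Simulation gives 85.1%, so the figure reproduces. The loss allowance also agrees: 24/(1 − 0.20) = 30. The 86% is for an unadjusted gating-outcome correlation.

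**How often the rule fires.** I read it as two tests at 0.05 (arms differ on baseline; baseline correlates with outcome) and simulated it with 24 per arm and rho 0.5 to 0.7. Both conditions were met in about 5% of trials.

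**Precision.** Adjustment multiplies the residual variance by 1 − rho². An effect of d = 0.826 has 80% unadjusted power with 24 per arm (noncentral t, 46 df). With adjustment the effect becomes d/√(1 − rho²), on 45 df:

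| rho | 1 − rho² | d/√(1 − rho²) | Power |
|---|---|---|---|
| 0.3 | 0.91 | 0.87 | 83.5% |
| 0.4 | 0.84 | 0.90 | 86.3% |
| 0.5 | 0.75 | 0.95 | 89.9% |
| 0.6 | 0.64 | 1.03 | 93.8% |
| 0.7 | 0.51 | 1.16 | 97.5% |

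**Gating main effect.** Simulation of 4,000 trials with 48 patients and a linear model with treatment and gating. Gating has no link to week-12 performance beyond baseline. Nominal rate 5%:

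| r | rho | Unadjusted | Baseline included |
|---|---|---|---|
| 0.2 | 0.5 | 10% | 5% |
| 0.3 | 0.5 | 17% | 5% |
| 0.3 | 0.7 | 31% | 6% |
| 0.5 | 0.5 | 40% | 4% |

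**Within the medication arm** (n = 24, 5,000 trials). The correlation induced between gating and outcome is r × rho, for example 0.5 × 0.7 = 0.35. False positives were 10% at r = 0.3, rho = 0.5; 39% at r = 0.5, rho = 0.7; and 72% at r = rho = 0.7. With baseline included they were about 5%.

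**Treatment-by-gating interaction** (48 patients, 5,000 trials). With the same baseline slope in both arms, false positives stay near 5% with or without the baseline score. If treatment changes that slope by 0.5 (rho = 0.5):

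| r | No baseline | Baseline main effect | Plus baseline-by-treatment |
|---|---|---|---|
| 0.5 | 11% | 15% | 5% |
| 0.7 | 20% | 24% | 5% |

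A baseline main effect alone therefore does not protect the interaction in that case.

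**The case against.** The strongest reply is that the protocol already contains the requested rule. C.4.7 is the one place that names week-12 performance as an outcome, and it promises the covariate without condition in the preceding sentence. A reader of C.4.20 and the SAP alone might infer that the plan chose to withhold the baseline. The documents do not support that: they contradict each other. But C.4.7 sends the reader to C.4.20, where the rule is conditional, and the SAP has only the conditional rule. The contradiction therefore has a practical effect.

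Second, the regression on treatment, gating and their interaction is written for TES. A reader might infer that this model is defective for lacking a baseline score. That does not follow: the promised covariate is the baseline value of the week-12 performance outcome, which is not TES. What is missing is any written model for week-12 performance.

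Third, a reader might infer that the plan's key test, the interaction, is biased. The simulations show that it is not when baseline slopes are equal across arms. The false-positive concern is confined to a gating main effect or a within-arm correlation.

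Fourth, the magnitudes are illustrative. Both correlations are assumed, d = 0.826 was chosen to give 80% power and is not a plan figure, and 24 per arm counts usable scans before any dropout by week 12. All of this stands.

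Finally, week-12 performance is not among the outcomes in C.3.4, whose primary measure is urine-based. That limits the importance of the point. It does not remove it, because C.4.7 declares the score a treatment outcome for the prediction analysis.

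**Conclusion.** The point holds for the week-12 task-performance outcome only. C.4.20 and the SAP contradict C.4.7 on its baseline score, and the conditional rule suits neither precision nor control of gating-baseline confounding. The roughly 5% trigger rate applies to a comparison of the randomised arms; C.4.20 does not define which groups are meant, and the rate would not apply to patients against controls.

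The loss of precision is certain in direction if rho is not zero. It is modest at rho 0.3 (80% to about 84%) and large at 0.7 (about 98%). The false-prediction risk needs both correlations to be non-zero: 17% to 40% in 48 patients for r of 0.3 to 0.5 with rho 0.5. The interaction is at risk only if treatment changes the baseline slope. This should be corrected, but it does not touch the primary outcome or the TES analysis.

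**What to change.** In C.4.20 and the SAP, carry the C.4.7 commitment through:

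- Any model with week-12 task performance as the outcome always includes the pre-treatment out-of-scanner score on the same task, whether or not groups differ on it, and the adjusted model is the one reported.
- When the treatment-by-gating interaction is tested for this outcome, a baseline-by-treatment term is added.
- The rule based on a detected group difference does not apply to the outcome's own baseline.

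The cost is a short addition to each document and one or two degrees of freedom. C.4.14 already schedules the pre-treatment behavioural measurement on Day 2, so no new data are needed. The TES model stays as written.

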unpublished pilot data (Section C.2.4) have shown that the baseline fMRI working memory activation and the effective connectivity elicited by the working memory task are predictive of treatment outcome with DA enhancing medications in COs. Previous studies have shown that cocaine use can induce impaired response inhibition in both human ([1-8] and see [9] for review) and animals ([10-12] and see [13] for review). In addition, there is evidence ([15-19] and see [20, 21] for review) supporting the hypothesis that DA modulates response inhibition. Furthermore, impulsive personality traits predict DA-dependent changes in frontostriatal activity during component processes of working memory [117]. A study [100] conducted by our group has shown that trait impulsivity is predictive of cocaine addiction treatment outcome. *The relationship between cognitive domains and DA is relevant because the major objective of this study is to predict treatment outcome of DA enhancing medications.*

**Summary of Significance:** (a) Establishing the directional relationship between PFC and striatum and the role of striatal gating in cocaine treatment response will significantly improve our understanding of dopaminergic and pharmacotherapeutic mechanisms in COs. (b) The pilot data (Section C.2.4) suggest that treatment outcome in COs with low pretreatment striatal OA can be improved with OA enhancing treatments by increasing striatal OA function, which we theorize increases striatal gating of cortico-cortico connections. Thus the evidence supporting the hypothesized striatal gating mechanism will have significant implication in cocaine addiction treatment. (c) An issue in cocaine dependence research is the lack of clinically useful biomarkers for pharmacotherapies. Effective connectivity as measured by snOCM may ultimately lead to clinically useful biomarkers for cocaine dependence and its treatment.

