
probability that it exceeds some number (e.g., for Poisson regression a Risk Ratio of 1.0). Specification of vague neutral priors will reflect uncertainty regarding parameter values, utilizing prior distributions for the lower order effects that are neutral and diffuse with specification  $-N(0, 1 \times 10^{-6})$  on the log scale (i.e., centered at the null hypothesis with a 95% Credible Interval of  $\pm 1960$ ) for all coefficients, and  $-U(0, 100)$  for any required dispersion terms. Examination of the interaction of treatment and the subgroup index forms the crux of the evaluation of the subgroup effect. For evaluating the interaction representing the differential subgroup effect, analysis will be conducted in two ways: (a) utilizing diffuse, indifferent priors  $(-N(0, 1 \times 10^{-6})$  on the log scale for the interaction coefficients, and (b) using informative skeptical priors for the coefficients will evaluate sensitivity of statistical conclusions to specification of priors. Informative, skeptical priors will be derived via the method first proposed by Dixon and Simon [200]. Evaluation of resulting posterior distributions will permit conclusions regarding the probability that subgroup/interaction effects of varying magnitudes obtain. Examples of this use of the posterior distribution may be found in Green et al. [197]. Bayesian modeling will use SAS v9.2 (Proc Genmod and Proc Monte-Carlo Markov chain [MCMC]), and in WinBugs 1.4.3 (<http://www.mrc-bsu.cam.ac.uk/bugs>). Convergence of Bayesian analyses on the posterior distributions via MCMC will be assessed via graphical (Trace Plot, Autocorrelation Plot) and quantitative (Geweke Diagnostics, Gelman-Rubin Diagnostics, and Heidelberger-Welsh Diagnostics) evidence. Evaluation of posterior distributions will permit statements regarding the probability that effects of varying magnitudes exist, given the data.

While the use of urn randomization [153] will likely result in comparable groups, substantial heterogeneity may still exist within conditions on baseline variables such as severity, duration of use, and impulsivity. We propose subgroup analyses following the procedures described above. This will determine the degree to which baseline variables moderate the interaction of treatment and snOCM.

Specific Aim 3: To conduct an snOCM of impulsivity to test Hypotheses 1 and 2 (above).

The statistical analysis is essentially the same as in Specific Aims 1 and 2.

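### The Aim 2 robustness check, read as a main-effect covariate, cannot remove bias in the treatment-by-gating interaction from a baseline variable that tracks gating and modifies the drug effect

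*Protocol*

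**What the plan says.** Protocol C.4.20, Specific Aim 2, sets the model: "Regression of treatment, averaged gating, and their interaction will permit evaluation of differential treatment response as function of gating". It then says which term counts: "The critical element in doing so is the evaluation of the interaction term".

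The confounding rule is in the same section. It has a trigger, "Pretreatment task behavioral performance or demographic variables on which group differences are detected, and which are correlated with outcomes, meet the definition of confounders", and an action, "analyses will evaluate the robustness of findings after statistically controlling for the confounder". The result is then sorted: "If conclusions remain unchanged after covarying for the confounder, the more parsimonious model will be reported", with a robustness statement attached. If the conclusion changes, both models are reported. The SAP (Data analysis plan) repeats this text. Neither document names a covariate-by-treatment term in the rule. Protocol C.4.7 says that pretreatment performance is controlled as a covariate, which supports the main-effect reading.

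Two other parts of the plan bear on the point. The initial analyses in C.4.20 look at correlations between baseline variables and the connectivity results, but do not feed the rule. C.4.20 and the SAP also plan subgroup analyses for variables such as severity, duration of use and impulsivity, of which the protocol says: "This will determine the degree to which baseline variables moderate the interaction of treatment and snOCM". Aim 3 reuses the Aim 1 and Aim 2 analyses.

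**The concern.** Treatment is randomised; gating is measured. The treatment-by-gating coefficient can therefore be non-zero because some other baseline variable, correlated with gating, is the real modifier of the drug effect. A robustness check is useful only if it can expose that. A main-effect covariate absorbs the variable's average slope on outcome, but not the difference in slope between arms, and that difference is what leaks into the interaction.

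At stake is the mechanistic claim. The Aim 2 statement treats gating as a reflection of low dopamine, and the Summary of Significance says that evidence for the gating mechanism would have treatment implications. That needs an interaction that is not carried by another modifier. The protocol gives some reason to ask: section A.6 states that "impulsive personality traits predict DA-dependent changes in frontostriatal activity during component processes of working memory" and also reports that trait impulsivity predicts cocaine treatment outcome.

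**Working it through.** **The plan's own figure for the interaction.** C.4.20 puts interaction power at about 29% when a main effect of the same size has 80%. With the interaction SE twice the main-effect SE, power = Φ((1.960 + 0.842)/2 − 1.960) = Φ(−0.559) = 28.8%. It reproduces.

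**Algebra.** Take equal arms, with gating G and covariate C standardised and correlated at rho. Outcome depends on C with slope b0 on placebo and b1 = b0 + g on drug. G has no effect in either arm, so the true interaction given C is 0.

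- *C omitted.* The slope on G in arm t is rho × b_t. The interaction is rho × (b1 − b0) = rho × g.
- *C as a main effect with common slope c.* The normal equations give a_t = rho × (b_t − c) for the slope on G in arm t, and (b0 + b1 − 2c)(1 − rho²) = 0, so c = b0 + g/2. Then a1 = rho × g/2, a0 = −rho × g/2, and the interaction is again rho × g.
- *C and C × treatment.* Each arm is fitted with its own slope on C, so a0 = a1 = 0. The bias is gone.

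**Simulation at the planned size** (24 per arm, C.4.1). Linear outcome, residual SD 1, average slope on C of 0.5, true interaction 0, two-sided 5% test. The documents give neither rho nor g, so both are assumed. Each cell lists the unadjusted model / C added / C and C × treatment added.

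| rho | g | Mean interaction | Rejection, % |
|---|---|---|---|
| 0.3 | 0.5 | 0.15 / 0.14 / 0.00 | 7.3 / 7.3 / 4.6 |
| 0.5 | 0 | 0.00 / 0.00 / 0.00 | 5.5 / 5.2 / 5.8 |
| 0.5 | 0.5 | 0.25 / 0.25 / 0.00 | 11.0 / 12.5 / 4.4 |
| 0.5 | 1.0 | 0.51 / 0.50 / 0.00 | 29.6 / 31.4 / 5.2 |
| 0.7 | 1.0 | 0.70 / 0.70 / 0.00 | 52.3 / 56.0 / 5.0 |
| 0.7 | 1.5 | 1.05 / 1.05 / 0.00 | 80.2 / 83.0 / 5.2 |

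Rejection after covarying can exceed the unadjusted rate, because residual variance falls while the bias stays.

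**Count outcome.** TES is a count. In a negative binomial model (assumed mean 12, dispersion 0.5) with rho = 0.5 and a covariate-by-treatment log rate ratio of 0.8, the interaction rate ratio is 1.47 unadjusted, 1.48 with C and 0.99 with the product. The algebra predicts exp(0.5 × 0.8) = 1.49 for the first two.

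**How often the rule would fire.** Reading both parts of the trigger as p < 0.05 (assumed), it is met in about 3–5% of simply randomised trials per variable. Among trials where it is met, the conclusion is unchanged by covarying in 96–98% when g = 0, and in 90–95% when g is 0.5 to 1.0. Passing the check therefore says little about whether this bias is present.

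Among those same trials, an interaction significant in both models, and so called robust although the true value is 0, occurs in 3–46% for rho 0.3–0.7 and g 0.5–1.0, against 2–4% when g = 0. Multiplying through at the two ends: 800/16,932 = 4.7% × 3.0% = 0.14%, and 800/18,397 = 4.3% × 46% = 2.0% of all trials, per variable.

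**The case against.** Several arguments on the other side carry weight.

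- *Scope of the rule.* It covers task performance and demographic variables. The Barratt Impulsiveness Scale (BIS) and cocaine-use severity are neither; both are urn-balancing variables (C.3.2), so arm differences in them are made less likely by design. A robustness statement would seldom be issued for them. This stands, and it limits how often the error could occur. It also means that the variables most likely to matter usually go unchecked.
- *Prediction needs no adjustment.* The objective in C.1 is to predict treatment response. If gating stands in for a true modifier, it still predicts differential response, and the unadjusted interaction is valid for that use. This stands; the point is confined to the mechanistic reading.
- *Form of adjustment.* Statistical control does not rule out a product term. True: the form is unspecified, and main-effect entry is the natural reading, not a stated one.
- *The moderation analyses.* A hierarchical three-way model for severity, duration or impulsivity would contain that variable's product with treatment. True, but those models answer a three-way question and the robustness statement does not rest on them.
- *Inference.* The plan uses posterior probabilities, under both diffuse and sceptical priors. The rejection rates above do not carry over directly, and sceptical priors would shrink a spurious interaction. Under diffuse priors the bias in the coefficient remains.

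A reader might infer that the plan will certify a confounded Aim 2 result, with impulsivity or severity as the likely culprit. The documents do not support that. They give no correlation between any baseline variable and the gating parameter. Section A.6 links impulsivity to frontostriatal activity and to outcome, but does not show that it modifies the benefit of levodopa/carbidopa.

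**Conclusion.** The point holds as a conditional one. If a baseline variable correlates with gating and modifies the drug effect, main-effect adjustment leaves a bias of rho × g in the interaction, in linear and count models alike, and the plan could describe that interaction as robust. If either condition fails, there is no such bias.

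Where the bias exists it can be large: with main-effect adjustment, false rejection runs from 7% to 83% over the assumed range rho 0.3–0.7 and g 0.5–1.5 SD, against 4–5% with the product term. A false statement of robustness would be much rarer, roughly 0.1–2% per variable over rho 0.3–0.7 and g 0.5–1.0 SD, because the trigger seldom fires. Those figures rest on assumed rho, g and p-value cut-offs, on simple randomisation, and on frequentist tests standing in for the planned Bayesian analysis. The algebra needs none of these beyond equal arms and a linear model.

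The trigger and the form of adjustment both need to change. Widening the trigger alone would only yield more robustness statements from a check that cannot detect the problem.

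**What to change.** In C.4.20 and the SAP, for Aims 2 and 3:

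1. State that the robustness model enters both the baseline variable and its product with treatment.
2. Apply it whatever the arm balance, one variable at a time, to a short prespecified list already collected, for example cocaine-use severity, BIS and pretreatment task performance.
3. Report the treatment-by-gating estimate with its interval from the unadjusted and the adjusted model.
4. Base any robustness statement on how far the estimate moves, not on whether it stays significant.
5. Say that this supports the mechanistic reading; the unadjusted interaction remains the result for prediction.

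The cost is SAP wording, one product term per variable, and a wider interval for the adjusted interaction: an SE about 10–16% larger at rho = 0.5 and 35–41% larger at rho = 0.7, in line with 1/√(1 − rho²) = 1.155 and 1.400. Starting from the plan's 29% power, SEs larger by 16% and 41% would leave Φ(1.401/1.16 − 1.960) = 23% and Φ(1.401/1.41 − 1.960) = 17%. Judging robustness by significance would therefore often label a true effect as not robust, which is the reason for item 4. Keeping the list short matters with 48 patients analysed in the two arms. The primary model is untouched.
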